13.4.2. Reporting Adverse Events to the Responsible IEC/IRB and Health Authorities

Adverse events that meet the IEC/IRB requirements for reporting must be reported within the IEC/IRB's written guidelines. Each clinical site will refer to and follow any guidelines set forth by their Approving IEC/IRB. Each clinical site will refer to and follow any guidelines set forth by their local governing Health Authorities.

The Sponsor will report applicable Adverse Events to the local health authorities according the written guidelines, including reporting timelines.

13.5. Event of Special Interest

None.

13.6. Reporting of Pregnancy

Subjects reporting pregnancy (by self-report) during the study will be discontinued after the event is recorded as an Adverse Event. Once discontinued, pregnant participants and their fetuses will not be monitored for study related purposes. Pregnant participants are not discontinued from contact lens or solution related studies for safety concerns, but due to general concerns relating to pregnancy and contact lens use. Specifically, pregnant women are discontinued due to fluctuations in refractive error and/or visual acuity that occur secondary to systemic hormonal changes, and not due to unforeseen health risks to the mother or fetus.

14. STATISTICAL METHODS

14.1. General Considerations

Statistical analysis will be undertaken by the study biostatistician. A general description of the statistical methods to be implemented in this clinical trial is outlined below.

All data summaries and statistical analyses will be performed using the SAS software Version 9.4 or higher (SAS Institute, Cary, NC⁶. Throughout the analysis of data, the results for each subject/eye will be used when available for summarization and statistical analysis. Unscheduled visits will be summarized separately and will be excluded from the statistical analysis.

Summary tables (descriptive statistics and/or frequency tables) will be provided for all baseline variables, efficacy variables, and safety variables as appropriate. Continuous variables will be summarized with descriptive statistics

(n, mean, standard deviation [SD], median, minimum and maximum). Frequency count and percentage of subjects or eyes within each category will be provided for categorical data.

14.2. Sample Size Justification

This study was not designed or powered to test any statistical hypotheses, as there was no available data for these endpoints and population. The sample size of 40 subjects to enroll with approximately 30 to complete was based on clinical considerations and operational feasibility to gain more understanding about the new wearers contact lens experience.

14.3. Analysis Populations

Safety Population:

All subjects who were administered any test article.

Per-Protocol Population:

All subjects who successfully complete all visits and do not substantially deviate from the protocol as determined by the trial cohort review committee prior to database hard lock. Justification for the exclusion of subjects with protocol deviations from the per-protocol population set will be documented in a memo to file.

Intent-to-Treat (ITT) Population:

Intention-to-treat population will include all assigned subjects.

14.4. Level of Statistical Significance

Not applicable, there is no planned hypothesis testing for any study endpoints.

14.5. Primary Analysis

The primary analyses will be conducted on the safety population. The primary endpoint will be summarized using counts and percentages. The primary endpoints will be evaluated using the following clinical findings:

Incidence (percentage) of eyes with Grade 3 or 4 slit lamp findings related to the study lenses after 2-week of lens wear.

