2. STUDY OBJECTIVES, ENDPOINTS AND HYPOTHESES

2.1. Objectives

Primary Objective: The primary objective of this study is to estimate the incidence rate (percentage) of eyes with clinically significant slit-lamp findings (Grade 3 or 4) related to the study lens after approximately 2-weeks of lens wear.

Exploratory Objectives: The other objectives are to measure commitment to lens wear in neophyte subjects after approximately two weeks of wearing experience, measure Insertion & Removal (I&R) skills, evaluate new wearer confidence and motivation for lens wear, and assess lens performance (CLUE vision, comfort & handling scores).

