2.2. Endpoints

Primary Endpoint:

1. Percentage of eyes with slit-lamp findings (Grade 3 or 4) related to study lens wear:

Slit Lamp Findings (Grade 3 or higher) will be assessed for each subject eye at all study visits (scheduled and unscheduled). However, the primary endpoint will be the percentage of eyes with Grade 3 or higher SLFs related to study lens wear, after approximately 2 weeks of lens wear. SLFs will be evaluated and classified using the FDA Grading scale rating from 0 to 4, where Grade 0 represents the absence of findings and 1 to 4 representing successively worse findings (i.e., Grade 1=trace, Grade 2= mild, Grade 3=moderate and Grade 4= severe).

Other Exploratory Endpoints:

- 1. **Commitment to lens wear:** Do you want to continue to wear contact lenses after this study? (Response set: Yes, No)
- 2. **Reasons for Discontinuation** (if applicable): Which of the following is the main reason why you want to **stop** wearing contact lenses? (Response set: They were uncomfortable to wear, My eyes were too dry to wear them, I didn't like my vision with contacts, They were too difficult to put on and take off, They were more trouble than it's worth, I'm concerned about the cost, and Other reason [free text])

3. **Insertion Time:**

Insertion time is quantified as the total time (in minutes and seconds) it takes for the subject to insert both lenses (OU). Insertion time will be collected at the initial fitting, after approximately 1-week of wear, and after approximately 2-weeks of wear. The insertion time is a continuous endpoint.

4. Removal Time:

Removal time is quantified as the total time (in minutes and seconds) it takes for the subject to remove their lenses (OU) at three different time points – at the initial fitting, after approximately 1-week of wear, and after approximately 2-weeks of wear. The removal time is a continuous endpoint.

5. Confidence:

New wearer **confidence** (**for lens wear**) will be assessed at baseline (prior to lens fitting), post fitting, after approximately 1-week of wear, and after approximately 2-weeks of wear using the individual questionnaire item: How confident do you feel in your ability to successfully **put on** contact lenses? (Response Set: Not confident, A little confident, Somewhat confident, Confident, Highly confident). (Response Set: No confidence/Little Confidence/Some Confidence/Confident/High Confidence). New wearer confidence is an ordinal categorical endpoint.

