4.3. Enrollment Target and Study Duration

This study will have an enrollment target of approximately 40 subjects, and it is estimated that approximately 30 subjects will complete the study. The study will be conducted at up to 5 clinical sites, where the enrollment target for each site will be approximately 8 subjects. A subject will be considered enrolled upon signing of the informed consent/assent form.

The study enrollment period is approximately 8 weeks. Once enrolled, subjects will be in the study for about 2 weeks, making the total study duration about 10 weeks from the first subject first visit (FSFV) to last subject last visit (LSLV). Subjects who are discontinued prior to the final evaluation may be replaced at the discretion of the study sponsor. The investigation will end at the time that the study data is hard locked.

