2.12	Slit Lamp Biomicroscopy	FDA Slit Lamp Classification Scale will be used to grade the findings. If the subject has a Grade 3 slit lamp finding, it will be recorded as an Adverse Event and the subject will be monitored as per the guidelines given in section 13. If the clearance of the fluorescein needs to be expedited, preservative-free rewetting drops may be	
2.13	Lens Insertion (timed)	instilled. While being timed, the subject will re-insert the study lenses on their own, one at a time. Insertion: Using a stopwatch or a Timer App, observe the subject	
		and record how long it takes for them to insert each lens (one at a time). • Enter total insertion time OD • Enter total insertion time OS Total insertion time OU Note: • Insertion time starts when the subject first attempts to insert the lens (at the approach step) and stops when the lens is placed on eye. • You may ask the subject to let you know when the lens is in.	
2.14	Subjective Best Sphere Over Refraction (if applicable)	An over-refraction may be performed at the Investigators discretion. Perform subjective best sphere refraction over the study lenses with a phoropter, trial lenses, or flipper bars OD and OS. Record the best corrected distance visual acuity to the nearest letter (OD and OS).	
2.15	Lens Power Modification	Note: The subject may continue in the study if the over-refraction is Plano, at the Investigators discretion. Adjust the lens power if the subject's best sphere over-	
	(if applicable)	refraction is not Plano. Up to two power modifications are allowed.	
2.16	Subject Reported Ocular Symptoms (if applicable)	Subjects will respond to a verbal open-ended symptoms questionnaire.	
2.17	Exit VA	Record the subject's distance visual acuity, OD and OS, to the nearest letter.	

		Visit 2: Treatment 1 Follow-Up 1
Step	Procedure	Details
2.18	Continuance	For the subject to continue in the study, they must meet all three of the following criteria: • Visual acuity is 20/30 or better OD and OS. • The lens fit is acceptable OD and OS. • Investigator approval. If the Investigator does not approve the dispensing of the first study lens, then the study is terminated for that subject.

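### The primary objective is to estimate an eye-level rate, but 14.5 plans no confidence interval, 14.2 states no precision, and withdrawal after a Visit 2 finding could make the 2-week percentage too low

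*Combined protocol and SAP*

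**What the plan says.** Section 2.1 gives one primary objective: "to estimate the incidence rate (percentage) of eyes with clinically significant slit-lamp findings" that are related to the lens, after about two weeks of wear. Lenses are worn in both eyes, so each subject contributes two eyes.

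For the analysis, section 14.5 uses the safety population and states: "The primary endpoint will be summarized using counts and percentages". The general rule in 14.1 is similar: "Frequency count and percentage of subjects or eyes within each category will be provided for categorical data". Neither section mentions an interval, nor does any other part of the document. Sections 2.3 and 14.4 say that endpoints are descriptive and that no hypothesis is tested.

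On size, section 14.2 states: "The sample size of 40 subjects to enroll with approximately 30 to complete was based on clinical considerations and operational feasibility". It gives no assumed rate and no interval width. Section 4.3 adds: "A subject will be considered enrolled upon signing of the informed consent/assent form". Missing values are not imputed (14.9).

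On which examinations count, section 2.2 has findings graded at every scheduled and unscheduled visit but sets the endpoint at about 2 weeks. Section 14.1 says: "Unscheduled visits will be summarized separately and will be excluded from the statistical analysis". At Visits 2 and 3 (section 7.2, steps 2.12 and 3.14), "If the subject has a Grade 3 slit lamp finding, it will be recorded as an Adverse Event". Section 13.1 lists Grade 3 or higher corneal findings among significant adverse events. Section 8.2 withdraws subjects whose significant event requires lens wear to stop. Step F.4 of the Final Evaluation provides a slit-lamp examination for subjects who leave early, but 14.5 does not say whether that examination counts as the 2-week result.

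**The concern.** An objective of estimation needs a statement of uncertainty, and the plan provides none for its only primary endpoint. A zero or near-zero result is plausible, and a bare percentage does not show which true rates remain compatible with it. A reader who fills the gap by treating all eyes as independent may get a limit that is too small, because the two eyes of one subject can be correlated.

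A second, separate matter is who is in the percentage. A subject with a related corneal finding of Grade 3 or higher at Visit 2, where lens wear has to stop, is withdrawn before the 2-week examination. That loss depends on the outcome and can only lower the 2-week figure. Related findings at unscheduled visits are a different case: 14.1 keeps them out of the statistical analysis directly.

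**Working it through.** **The plan's own figure.** Section 14.2 derives nothing, so there is no calculation to reproduce. The numbers agree with each other: 5 sites × 8 subjects = 40, and 40 × 0.75 = 30. That does not give a precision.

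**Inputs.** From the documents: 40 subjects enrolled, about 30 completing, two eyes each (60 or 80 eyes). Assumed, because the documents give none of them: a two-sided 95% level, the between-eye correlation, and the true rates used below.

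**Exact limits.** For x affected of n, the Clopper-Pearson upper limit is the 0.975 quantile of Beta(x + 1, n − x). The lower limit is the 0.025 quantile of Beta(x, n − x + 1). With x = 0 the upper limit is 1 − 0.025^(1/n):

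- n = 30: 1 − 0.025^(1/30) = 11.57%
- n = 40: 1 − 0.025^(1/40) = 8.81%
- n = 60: 1 − 0.025^(1/60) = 5.96%
- n = 80: 1 − 0.025^(1/80) = 4.51%

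**Effect of pairing.** If fellow eyes are fully concordant, the subject is the real unit. Understatement is 1 − (eye limit / subject limit).

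| Subjects affected (both eyes) | Eyes as independent, upper limit | Subjects, upper limit | Understatement |
|---|---|---|---|
| 0 of 30 | 0/60: 5.96% | 11.57% | 48.5% |
| 0 of 40 | 0/80: 4.51% | 8.81% | 48.8% |
| 1 of 30 | 2/60: 11.53% | 17.22% | 33.0% |
| 1 of 40 | 2/80: 8.74% | 13.16% | 33.6% |
| 2 of 30 | 4/60: 16.20% | 22.07% | 26.6% |

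With uncorrelated eyes the understatement at zero events is nil. At an assumed correlation of 0.5, solving [(1 − p)² + 0.5·p(1 − p)]^N = 0.025 gives 7.9% (N = 30) and 6.0% (N = 40). An effective sample size of 2N/(1 + 0.5) gives 8.8% and 6.7%. The two methods differ, but both lie between the independent and the fully concordant limits.

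**How likely is zero?** The chance of no affected subject is (1 − p)^N. At a true subject rate of 1% it is 74% (N = 30) or 67% (N = 40). At 5% it is 21% or 13%.

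**What carries over to the eye rate.** When both eyes are assessed, the proportion of subjects affected in at least one eye cannot be smaller than the proportion of eyes affected. Its upper limit therefore bounds the eye rate under any between-eye correlation. The lower limit does not carry over: two one-eye cases in 30 subjects give 0.82% by subject but 0.41% for 2/60 eyes.

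**Outcome-related loss (illustrative).** Suppose 30 subjects are assessed at 2 weeks with no finding, and one more was withdrawn after a related finding at Visit 2.

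- 2-week result: 0/30, upper limit 11.6%.
- Any examination, no other non-completer examined: 1/31 = 3.2% (0.1% to 16.7%).
- Any examination, all 40 subjects examined at least once: 1/40 = 2.5% (0.1% to 13.2%).

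**The case against.** The plan is openly and consistently descriptive. It concerns a marketed lens in a single arm with no success criterion, section 21 plans no publication, and an exact interval could be computed at reporting if subject counts are shown. All of that stands, and it limits the weight of the point. But 2.3 and 14.4 rule out tests; an interval around an estimate is not a test.

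Several stronger readings are tempting and are not supported:

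- *That pairing of eyes invalidates the primary percentage.* It does not. The crude eye percentage is a valid point estimate; pairing affects only its uncertainty.
- *That a Visit 2 finding would go unreported.* It would not. It is recorded as an adverse event, 8.2 requires the current visit and the Final Evaluation to be completed, and 14.1 promises safety tables. What may be missing is its place in the primary percentage.
- *That the unscheduled-visit exclusion removes the Visit 2 case.* Visit 2 is a scheduled visit, so that sentence does not apply to it.
- *That every Grade 3 finding leads to withdrawal.* The entry in 13.1 concerns corneal findings, 8.2 applies where lens wear must stop, and 13.3 refers to the investigator's judgment on continuation.
- *That the number assessed must fall to 30.* Sections 4.3 and 8.2 allow replacement at the sponsor's discretion. Replacement restores the number, but not the outcome of the subject who left.

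It is also fair to object that an interval does not cure outcome-related loss, and that a subject-level interval describes a different quantity from the eye rate. Both are correct. The loss therefore needs its own summary, and only the upper limit should be carried over.

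**Conclusion.** The point holds as an omission that is cheap to repair. It is not an internal contradiction, and no decision depends on it. The sole primary objective is estimation, yet no interval and no precision are stated. With zero affected subjects, the 95% upper limit would be about 12% for 30 assessed and about 9% for 40. Independent-eye limits of 6.0% and 4.5% would be too small by anything from nil to about half, depending on a correlation that the documents do not give.

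Separately, withdrawal after a related corneal finding at Visit 2 could make the primary percentage too low. The illustration moves the result from 0% to between 2.5% and 3.2%. That rests on one assumed case and is not a forecast. Stating the method in advance fixes the interval and the denominator before the result is known.

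**What to change.** 1. **Section 14.5.** Keep the eye count and percentage as primary. Add the proportion of safety-population subjects with a related Grade 3 or 4 finding in at least one eye at about 2 weeks, with the number assessed and an exact Clopper-Pearson 95% interval. State that only the upper limit carries over to the eye rate, as a conservative bound under any between-eye correlation, and that it does not correct for outcome-related dropout.
2. **Sections 14.5 and 14.1.** Add a supplementary proportion with an exact interval. It counts related Grade 3 or 4 findings at any slit-lamp examination already collected after first lens exposure: Visit 1 fitting where done, Visit 2, Visit 3, unscheduled and early exit. Starting at first exposure and not at dispensing matches the safety population, since subjects handle and wear lenses during the Visit 1 learning session. Report how many safety-population subjects had no such examination. Label the result as incidence over the whole exposure period, and make an exception to the unscheduled-visit exclusion for this summary only.
3. **Section 14.2.** State that with zero affected subjects the 95% upper limit is about 12% for 30 assessed and about 9% for 40 assessed.

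The cost is two exact binomial calculations and a sentence or two in each section, with no new data, visits, subjects or tests. The drawbacks are slightly more analysis, a wider stated uncertainty, and a subject-level bound that is wider than needed if fellow eyes are not fully concordant. The any-examination proportion must not be read as the 2-week endpoint.

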8.2. Withdrawal/Discontinuation from the Study

A subject will be withdrawn from the study for any of the following reasons:

- Subject withdrawal of consent.
- Subject not compliant to protocol (e.g., subject wearing the lenses overnight).
- Subject lost to follow-up.
- Subject no longer meets eligibility criteria (e.g. the subject becomes pregnant).
- Subject develops significant or serious adverse events necessitating temporary or permanent discontinuation of study lens wear.
- Subjects who have experienced a Corneal Infiltrative Event (CIE).
- Subjects who have experienced a symptomatic ocular adverse event necessitating temporary or permanent discontinuation of study lenses.
- Investigator's clinical judgment regarding the subject safety reasons (that it is in the best interest of the subject to stop treatment).
- Subject not compliant with study lens wear schedule (e.g., subject doesn't wear study lenses at all between visits).

Subject not successfully dispensed due to lack of efficacy and safety including poor vision, poor comfort
or unacceptable fit.

For discontinued subjects, the Investigator will:

- Complete the current visit (scheduled or unscheduled).
- Complete the Final Evaluation, indicating the reason that the subject was discontinued from the study.
- Record the spherocylindrical refraction with best corrected distance visual acuity.
- Collect used test article(s) (worn or brought to the visit) from the subject and discard them, unless
 otherwise stated in section 7.2.
- Collect all unused test article(s) from the subject.
- Make arrangements for subject care, if needed, due to their study participation

Additional subjects may be enrolled if a subject discontinues from the study prematurely, at the Sponsor's discretion.

In cases where a subject is lost to follow-up, every possible effort must be made to contact the subject and determine the reason for discontinuation/withdrawal. The measures taken to follow up must be documented including two written attempts and a certified letter (or equivalent) as the final attempt.

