Diagnoses and conditions that are considered Ocular Significant Adverse Events include, but not limited to the following:

- Contact Lens Induced Peripheral Ulcer (CLPU)
- Significant Infiltrative Events (SIE)
- Superior Epithelial Arcuate Lesions (SEALs)
- Contact Lens-induced Acute Red Eye (CLARE)
- Any Temporary Loss of > 2 Lines of BCVA
- Other grade 3 or higher corneal findings, such as abrasions or edema
- Non-contact lens related corneal events e.g. Epidemic Keratoconjunctivitis (EKC)
- Asymptomatic Corneal Scar
- Any corneal event which necessitates temporary lens discontinuation > 2 weeks

Non-Significant Adverse Events – are defined as those events that are usually asymptomatic and usually do not warrant discontinuation of contact lens wear but may cause a reduction in wear time. However, the Investigator may choose to prescribe treatment as a precautionary measure.

Diagnoses and conditions that are considered Ocular Non-Significant Adverse Events include, but not limited to the following:

- Non-significant Infiltrative Event (NSIE)
- Contact Lens Papillary Conjunctivitis (CLPC)
- Superficial Punctate Keratitis (SPK)
- Conjunctivitis: Bacterial, Viral, Allergic
- Blepharitis
- Meibomianitis
- Contact Dermatitis
- Localized Allergic Reactions
- Any corneal event not explicitly defined as serious or significant adverse event, which necessitates temporary lens discontinuation < 2 weeks

Adverse Device Effect (ADE) – An ADE is an "adverse event related to the use of an investigational medical device."

NOTE 1: This definition includes adverse events resulting from insufficient or inadequate instructions for use, deployment, implantation, installation, or operation, or any malfunction of the investigational medical device.

NOTE 2: This definition includes any event resulting from use error or from intentional misuse of the investigational medical device.¹

Unanticipated Adverse Device Effect (UADE) – A UADE is any serious adverse effect on health or safety or any life-threatening problem or death caused by, or associated with, the test article, if that effect, problem, or death was not previously identified in nature, severity, or degree of incidence in the investigational plan, Investigator's Brochure or protocol, or any other unanticipated serious problem associated with the test article that relates to the rights, safety and welfare of subjects.

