Upon discovery of an AE that is deemed 'possibly related' or 'related' to the test article or study procedures (whether related to the visual system or not), an AE review form must be completed. Additional dated and initialed entries should be made at follow-up evaluations. Separate forms must be completed for each eye if the AE is bilateral.

In addition, if an infiltrate(s) is present, he/she will complete the Corneal Infiltrate Assessment eCRF. Where necessary, a culture of the corneal lesion will be collected to determine if the infection is microbial in nature. If cultures are collected, the date of culture collection and laboratory utilized will be recorded.

Changes in the severity of an AE shall be documented to allow an assessment of the duration of the event at each level of intensity to be performed. Adverse events characterized as intermittent require documentation of the onset and duration of each episode. Changes in the assessment of relationship to the Test Article shall also be clearly documented.

Subjects who present with an adverse event shall be followed by the Investigator, within licensure, until all signs and symptoms have returned to pre-treatment status, stabilized, or been satisfactorily resolved. If further treatment beyond licensure is required, the patient will be referred to the appropriate health care provider. The Investigator will use his/her clinical judgment as to whether a subject reporting with an adverse event will continue in the study. If a subject is discontinued from the study, it will be the responsibility of the Investigator to record the reason for discontinuation. The Investigator will also document the adverse event appropriately and complete the Adverse Event eCRF. Any subjects with ongoing adverse events related to the test article, study treatment or study procedures, as of the final study visit date, should be followed to resolution of the adverse event or until referral to an appropriate health care provider, as recommended by the Investigator. Non-ocular adverse events that are not related to the test article, study treatment, or study procedures may be recorded as "ongoing" without further follow-up.

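### Lens-related Grade 3 or 4 findings seen before Visit 3 can be left out of the only primary percentage

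*Combined protocol and SAP*

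**What the plan says.** Section 2.2 (Endpoints) first describes what is collected: "Slit Lamp Findings (Grade 3 or higher) will be assessed for each subject eye at all study visits (scheduled and unscheduled"). It then turns, with the word *However*, to what counts: "the primary endpoint will be the percentage of eyes with Grade 3 or higher SLFs related to study lens wear, after approximately 2 weeks" of wear. Section 14.5 (Primary Analysis) repeats the timing, "Incidence (percentage) of eyes with Grade 3 or 4 slit lamp findings related to the study lenses after 2-week of lens wear", and places the analysis on the Safety population, which section 14.3 defines as everyone given a test article.

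Section 14.1 (General Considerations) adds: "Unscheduled visits will be summarized separately and will be excluded from the statistical analysis". Section 14.9 rules out imputation and promises counts of missing values.

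Two other sections determine who reaches Visit 3. Section 8.2 lists among the reasons for withdrawal "Subject develops significant or serious adverse events necessitating temporary or permanent discontinuation of study lens wear". Section 13.1 includes in its list of ocular Significant Adverse Events "Other grade 3 or higher corneal findings, such as abrasions or edema". Withdrawal is not automatic, however. Step 2.12 of section 7.2 says of a Grade 3 finding at Visit 2 that "it will be recorded as an Adverse Event and the subject will be monitored as per the guidelines given in section 13", and section 13.3 says "The Investigator will use his/her clinical judgment as to whether a subject reporting with an adverse event will continue in the study".

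**The concern.** An incidence over two weeks of wear should count the eyes that had the event during those two weeks. As written, the percentage can be read as the share of eyes showing a finding at the Visit 3 exam. An eye that had a related Grade 3 or 4 finding at one week, and that was then withdrawn or had recovered, is not an eye with a finding at Visit 3.

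The omission can depend on the outcome itself. A corneal finding bad enough to stop lens wear is both a primary-endpoint type of event and a possible reason for the subject never to reach the exam that counts. This is the sole primary endpoint and there are no secondary analyses (14.6), so no other planned headline figure corrects it. The denominator is also open: the plan does not say whether Safety-population eyes without a Visit 3 exam are included.

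**Working it through.** **Step 1. Which exams can show a finding, and which feed the primary percentage?**

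| Exam | Performed under | Text on the primary percentage |
|---|---|---|
| Visit 2, about 1 week | 7.2, step 2.12 | No sentence includes it |
| Unscheduled visit | 7.3, step U.6 | 14.1 excludes it from the analysis |
| Early exit | 7.2, step F.4 | No sentence includes it |
| Visit 3, about 2 weeks | 7.2, step 3.14 | Included |

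**Step 2. Routes to omission.** (i) The subject is withdrawn before Visit 3, which 8.2 and 13.1 together allow. (ii) The subject stays and the finding resolves before Visit 3; no withdrawal is needed.

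**Step 3. Inputs.** Sections 4.3 and 14.2 give about 40 subjects enrolled and about 30 completing. The 40 agrees with 5 sites × 8 subjects, but it is a feasibility number with no rate or precision target behind it, so there is no sample size formula to reproduce. I assume that all 40 are exposed and examined at least once after dispensing (80 eyes) and that 30 have a Visit 3 exam (60 eyes). The 80 is an assumption: enrollment is counted at consent, so screen failures would lower it, and replacement of discontinued subjects (4.3, 8.2) could raise it. All event counts are assumed, because the documents give no event rate.

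**Step 4. Formulas.** Let *a* be the eyes with a related Grade 3 or 4 finding at Visit 3, and *b* the other eyes with such a finding only at an earlier exam.

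- Visit 3 reading, examined eyes: a/60
- Visit 3 reading, all Safety eyes: a/80
- Any post-dispensing exam: (a + b)/80

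**Step 5. Earlier findings, none at Visit 3 (a = 0).**

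| b | Visit 3 reading | Any exam, 80 eyes | Any exam, 70 eyes |
|---|---|---|---|
| 1 | 0/60 or 0/80 = 0% | 1/80 = 1.25% | 1/70 = 1.4% |
| 2 | 0% | 2/80 = 2.5% | 2/70 = 2.9% |
| 4 | 0% | 4/80 = 5.0% | 4/70 = 5.7% |

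The last column shows the effect of a smaller exposed group.

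**Step 6. Resolution alone.** Take 60 Safety eyes, all seen at Visit 3, with one Visit 2 finding that clears: 0/60 = 0% against 1/60 = 1.7%.

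**Step 7. Direction.** Take one finding at Visit 3 and none earlier (a = 1, b = 0).

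- Examined-eyes denominator: 1/60 = 1.7% against 1/80 = 1.25%, so the Visit 3 reading is too high. In general (a + b)/80 > a/60 requires 60(a + b) > 80a, that is b > a/3. Below that point the Visit 3 reading is the higher one.
- Full Safety denominator: a/80 is never above (a + b)/80, so the Visit 3 reading can only be too low.

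**Step 8. Chance that the case arises.** If each subject's risk of an early finding were 1%, 2% or 5% (assumed), the chance of at least one among 40 is 1 − (1 − p)^40 = 33%, 55% or 87%.

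**The case against.** The best reply is that *incidence*, on a Safety population that keeps early withdrawals, already means any finding up to two weeks. That reading is possible. But section 2.2 sets all-visit assessment against the two-week endpoint, and 14.1 would still remove unscheduled-visit findings on the cumulative reading.

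A second reply is that a fixed time point, stated consistently in the objective, the endpoint and the analysis, is a legitimate design choice. It is. A sponsor who wants that quantity should say so, call it the percentage at Visit 3 and define its denominator.

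A third reply is that little hangs on the number. The lens is marketed, nothing is tested, and exact 95% limits (treating eyes as independent) overlap widely: 0/60 has an upper limit of 5.96%, and 1/80 runs from 0.03% to 6.77%. This stands as a limit on the consequence. It does not settle which number to report.

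A reader might also infer that these events vanish from the study. The documents do not support that. Grade 3 findings at Visit 2 are recorded as adverse events, early leavers get an exit slit lamp exam, unscheduled visits are summarized separately, safety variables are tabulated and missing counts are shown.

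**Conclusion.** The concern holds for the primary percentage and no further. The stated timing and the unscheduled-visit exclusion can drop related Grade 3 or 4 findings from the numerator, and no other passage puts them back. Under the assumed 80 and 60 eyes, one to four such eyes separate a reported 0% from 1.25% to 5.0%. With so few eyes, a single one decides whether the headline is zero.

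Two stronger readings should be resisted. One is that a Grade 3 finding forces withdrawal: the combination of 8.2 and 13.1 makes it possible, but step 2.12 and 13.3 leave room to continue. The other is that the percentage must be too low: that follows only with the full Safety denominator, whereas counting only examined eyes can push it up.

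The wording should be settled before database lock. The plan has no hypothesis or decision rule that would turn on it.

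**What to change.** In 14.5, state that an eye enters the numerator if a related Grade 3 or 4 slit lamp finding is recorded at any scheduled, unscheduled or early-exit (F.4) exam after dispensing, up to and including Visit 3. State that the denominator is all Safety-population eyes with at least one post-dispensing exam, and show the number of Safety eyes without one.

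In 14.1, add that the exclusion of unscheduled visits does not apply to this endpoint. Report the Visit 3-only percentage beside the primary figure, with the number of eyes lacking a Visit 3 exam.

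List findings from the Visit 1 learning session separately. Those exams are optional and prompted by a red or irritated eye (steps 1.18 and 1.19), so they should not decide whether an eye enters the numerator or denominator.

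The cost is a few sentences, one extra table row, a short listing and slightly more analysis work. The exams are already in the protocol, so no new data are needed. The reported rate may shift slightly.
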